12.3 EFFICACY ANALYSIS

Analysis of Primary Endpoint

CONFIDENTIAL AND PROPRIETARY

This document contains information that is confidential and proprietary to Smith & Nephew PLC and Smith & Nephew, Inc. and is intended for use only by Smith & Nephew and its manufacturer. It shall not be reproduced or copied in whole or in part, nor shall the contents be disclosed by any means without prior written permission from Smith & Nephew, nor shall anyone make any use of it that is contrary to the expressed or implied wishes of Smith & Nephew.

Study Protocol—Device	
Safety and Performance of PEEK Anchors (DYNOMITE°, SPYROMITE°, RAPTORMITE°, FOOTPRINT° ULTRA PK SL) in Extremities	Number: 2018.15.SMD.PEEK.RET.EXT
	Version: 2.0 05Dec2018
	Page: Page 29 of 54

The rate (%) of clinical success of all the anchor devices combined at 6 months post-operative will be summarized as a frequency and a percentage. A 95% two-sided exact CI for a single proportion will be presented using Clopper-Pearson’s method (1934). The same type of analysis will be carried out for each of the anchors used in the study. These analyses will be carried out using the per protocol population as the primary analysis population with the safety population used for sensitivity analysis.

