13. SAMPLE SIZE JUSTIFICATION

This study is precision-based, thus, the sample size is not based on statistical power calculations. The sample size for this study is determined based on the feasibility of recruitment, enrollment and follow-up considerations. The study is therefore not powered for any statistical hypothesis testing but to have sufficient number of subjects to be able to estimate a clinical success rate of 91% with a 95% confidence interval (CI) of 80% to 100%.

With an assumption of a 91% clinical success rate to be obtained in each of the PEEK anchors and a corresponding 95% CI between 80% and 100%, enrolling between 20 and 120 subjects for each anchor's precision analysis is expected to provide between 15.2% to >95% probability, pending that there is sufficient volume of each type of anchor available. Thus, an overall minimum of 80 and maximum of 480 subjects are to be enrolled into the study, pending that there is sufficient volume of each type of anchor available. Additionally, a minimum of 10 subjects will be enrolled at any investigational site.

CONFIDENTIAL AND PROPRIETARY

This document contains information that is confidential and proprietary to Smith & Nephew PLC and Smith & Nephew, Inc. and is intended for use only by Smith & Nephew and its manufacturer. It shall not be reproduced or copied in whole or in part, nor shall the contents be disclosed by any means without prior written permission from Smith & Nephew, nor shall anyone make any use of it that is contrary to the expressed or implied wishes of Smith & Nephew.

Study Protocol—Device	
Safety and Performance of PEEK Anchors (DYNOMITE [®] , SPYROMITE [®] , RAPTORMITE [®] , FOOTPRINT [®] ULTRA PK SL) in Extremities	Number: 2018.15.SMD.PEEK.RET.EXT
	Version: 2.0 05Dec2018
	Page: Page 31 of 54

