Safety and Performance of PEEK Anchors (DYNOMITE[°], SPYROMITE[°], RAPTORMITE[°], FOOTPRINT[°] ULTRA PK SL) in Extremities	Number: 2018.15.SMD.PEEK.RET.EXT
	Version: 2.0 05Dec2018
	Page: Page 53 of 54

	would provide between 15.2% to 71% probability. Thus, an overall minimum of 60 and maximum of 120 subjects would be enrolled into the study. Additionally, a minimum of 10 subjects would be enrolled at any investigational site.	95% CI between 80% and 100%, enrolling between 20 and 120 subjects for each anchor's precision analysis is expected to provide between 15.2% to >95% probability, pending that there is sufficient volume of each type of anchor available. Thus, an overall minimum of 80 and maximum of 480 subjects are to be enrolled into the study, pending that there is sufficient volume of each type of anchor available. Additionally, a minimum of 10 subjects will be enrolled at any investigational site.
Section 14.2 Reporting Procedures	14.2: For ADEs and DevDs, details of the product/procedure related to the event will be included and where applicable, pictures taken of the device. The deficient product should be retained for return to the sponsor unless it is contaminated (e.g. used dressings must not be retained). Updates to submitted information will be recorded in the CRF within 24 hours of the information being available to the Investigator.	14.2 Removed language regarding pictures and retained product as it is not applicable to this retrospective chart abstraction study design: For ADEs and DevDs, details of the product/procedure related to the event will be recorded in the CRF within 24 hours of the retrospective chart review
Section 14.3 Follow-up of Subjects with Adverse Events	14.3: For subjects who are experiencing an ongoing unresolved AE at the time of their study completion or early discontinuation from the study, it is recommended that the Investigator schedule an appropriate follow-up visit	14.3 Clarified that follow-up is not a study procedure as this study is retrospective chart abstraction only: For subjects who are experiencing an ongoing unresolved AE at the time of their study completion or early discontinuation from the study, it is recommended that the investigator

CONFIDENTIAL AND PROPRIETARY

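### With the planned exact interval, Section 13's range of 15.2% to >95% does not hold across 20 to 120 subjects per anchor, and the precision event behind it is not defined

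*Combined protocol and SAP*

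**What the plan says.** Section 13 calls the study precision-based and states that the sample size comes from feasibility, with no hypothesis test. Its single precision statement starts "With an assumption of a 91% clinical success rate to be obtained in each of the PEEK anchors", adds "a corresponding 95% CI between 80% and 100" (percent), and concludes, for "enrolling between 20 and 120 subjects for each anchor", that the "precision analysis is expected to provide between 15.2% to >95% probability". The same sentence appears as revised text in the amendment log (23.1.4). Neither place writes out the event whose probability is meant.

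Section 12.3 fixes the interval: "A 95% two-sided exact CI for a single proportion will be presented using Clopper-Pearson"'s method. It also applies it per anchor: "The same type of analysis will be carried out for each of the anchors used in the study".

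The amendment log shows that the superseded version 1.0, for 20 to 40 subjects per anchor, "would provide between 15.2% to 71% probability". That text is no longer in force. It is used below only to help identify how the figures were obtained.

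**The concern.** A range of probabilities is attached to a range of enrolment counts, so the natural reading is that any permitted count from 20 to 120 gives a probability inside the range. An exact binomial interval does not behave that way. While the number of tolerated failures stays fixed, each added subject makes the target harder to reach, and the probability jumps up only when one more failure becomes tolerable. The value at the smallest n need not be the smallest value.

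This is the only probability the plan offers for its precision. The final count per anchor is open, since three of the four anchors are to be enrolled only if available. A reader who applies the range to an anchor that ends with slightly more than 20 subjects may be misled. Without a defined event, the reader also cannot tell whether the upper figure is right.

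**Working it through.** **Inputs.** True success rate p = 0.91 and target interval 80% to 100% (Section 13); n from 20 to 120 per anchor (Synopsis and Section 13); two-sided 95% Clopper-Pearson interval, per anchor (Section 12.3).

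**Formula.** For x successes out of n, the lower limit L is the 2.5% quantile of Beta(x, n−x+1) and the upper limit U is the 97.5% quantile of Beta(x+1, n−x), with U = 1 when x = n. The probability sought is the sum of the Binomial(n, 0.91) probabilities over all x whose interval meets the target.

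**Three readings of the target.**
- A: the interval lies between 80% and 100%, so L ≥ 0.80. This is the literal wording.
- B: width at most 22 points, from an average half-width of 91 − 80 = 11 points.
- C: width at most 20 points, from 100 − 80 = 20.

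**Reproducing the plan's figures.** At n=20, the result 20/20 has L = 0.8316 and width 1 − 0.8316 = 0.1684. The result 19/20 has L = 0.7513 and width 0.9987 − 0.7513 = 0.247. Only zero failures qualify under A, B and C, so the probability is 0.91^20 = 0.1516, the plan's 15.2%. At n=120, B and C give about 100%, which agrees with >95%, while A gives 92.7%, which does not. At n=40, B gives 71.0%, matching the superseded 71%; C gives 50.9% and A gives 28.9%. With the planned interval, B is the reading that matches every figure.

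**Just above n=20.**
- Under A, one failure is first tolerated at n=26: 24/25 has L = 0.7965 and 25/26 has L = 0.8036. From 20 to 25 the probability is 0.91^n, ending at 0.91^25 = 0.0946. At 26 it is 0.91^26 + 26 × 0.09 × 0.91^25 = 0.3076.
- Under C the switch is also at 26: 24/25 has width 0.999 − 0.7965 = 0.2025, and 25/26 has 0.999 − 0.8036 = 0.1954.
- Under B the switch comes at n=23: 21/22 has width 0.9988 − 0.7716 = 0.227, and 22/23 has 0.9989 − 0.7805 = 0.218. So 0.91^22 = 0.1256 at n=22, then 0.91^23 + 23 × 0.09 × 0.91^22 = 0.3742 at n=23.

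| n | A: L ≥ 80% | B: width ≤ 22 points | C: width ≤ 20 points |
|---|---|---|---|
| 20 | 15.2% | 15.2% | 15.2% |
| 21 | 13.8% | 13.8% | 13.8% |
| 22 | 12.6% | 12.6% | 12.6% |
| 23 | 11.4% | 37.4% | 11.4% |
| 24 | 10.4% | 35.1% | 10.4% |
| 25 | 9.5% | 32.9% | 9.5% |
| 26 | 30.8% | 30.8% | 30.8% |
| 40 | 28.9% | 71.0% | 50.9% |
| 119 | 93.2% | about 100% | about 100% |
| 120 | 92.7% | about 100% | about 100% |

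Over every n from 20 to 120, the counts below 15.2% are 21 to 25 under A and C, and 21 to 22 under B. The maximum under A is 93.2%, so >95% is not reached at any permitted count.

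**The case against.** The best defence is that the sentence pairs end values: 15.2% belongs to n=20 and >95% to n=120. Under B and C both are correct, and the plan never says that 15.2% is a minimum or that the probability rises steadily. This stands as far as the end values go. It does not rescue the wording, which attaches one range to another without saying that only the ends are meant, and it fails at the upper end under A.

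A second defence is that little depends on the number. The study tests no hypothesis, no decision rule uses the 15.2%, and a reader told 15.2% already knows that precision at the minimum is poor. This stands, and it keeps the point to a correction of the stated figure.

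A third is that another interval could lie behind the figures. A Jeffreys interval with width at most 20 points also gives 15.2% at n=20, 71.0% at n=40 and about 100% at n=120, and its minimum over 20 to 120 is the 15.2% at n=20. Section 12.3 names Clopper-Pearson, however, so that calculation would describe an interval the study will not report.

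Three stronger inferences are tempting and not supported:
- That 9.5% at n=25 is the established low point, and that one more chart triples the chance. This holds under A and C. Under B, which fits all the figures, n=25 gives 32.9% and n=26 gives 30.8%.
- That an anchor should be carried on to 26 subjects and not closed at 21 to 25. Under B, 23, 24 and 25 all do better than 26. The primary analysis is also per protocol, on chart data collected as available, so an enrolled count does not fix the analysed count.
- That the anchors enrolled only if available are likely to end at 21 to 25. The documents give no volume forecast.

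**Conclusion.** The stated range is wrong as a description of 20 to 120 subjects per anchor. With the planned interval and a true rate of 91%, its lower end is overstated under all three readings: by 15.2 − 12.6 = 2.6 points for a width of at most 22 points, and by 15.2 − 9.5 = 5.7 points for the other two. Its upper end is wrong only under the literal reading, where the maximum is 93.2%. The shortfall at the lower end is local: no count above 22 (reading B) or above 25 (readings A and C) falls below 15.2%.

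The documents do not settle which event was meant. The width of at most 22 points is the best match, partly because of a superseded figure, but that is an inference. The finding does not invalidate the design or the planned analysis. It concerns the accuracy of the plan's only precision probability.

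**What to change.** In Section 13, state the precision event in words or as a formula, name the Clopper-Pearson interval as the basis, and replace the range with exact probabilities at named counts for the chosen event:

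- Lower limit at least 80%: 15.2% at n=20, 9.5% at 25, 30.8% at 26, 28.9% at 40, 92.7% at 120. The claim of more than 95% is then removed.
- Width at most 22 points: 15.2% at n=20, 12.6% at 22, 30.8% at 26, 71.0% at 40, about 100% at 120.

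If a width of at most 20 points was meant, use column C of the table above. In each case, add that the probability does not rise steadily with n. No rule on when to close enrolment is needed.

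The cost is one sentence or a small table, with a slightly less favourable stated figure. Sample size, data collection and analysis stay as they are.
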